8. ADVERSE EVENTS

8.1. DEFINITIONS

Adverse Event (AE): any untoward medical occurrence in a patient or clinical study subject.

Serious Adverse Event (SAE): any untoward and unexpected medical occurrence or effect that:

- Results in death
- Is life-threatening – *refers to an event in which the subject was at risk of death at the time of the event; it does not refer to an event which hypothetically might have caused death if it were more severe*
- Requires hospitalisation, or prolongation of existing inpatients' hospitalisation
- Results in persistent or significant disability or incapacity
- Is a congenital anomaly or birth defect

Medical judgement should be exercised in deciding whether an AE is serious in other situations. Important AEs that are not immediately life-threatening or do not result in death or hospitalisation but may jeopardise the subject or may require intervention to prevent one of the other outcomes listed in the definition above, should also be considered serious.

8.2. REPORTING PROCEDURES

All adverse events will be recorded in the Case Report Form (CRF). Depending on the nature of the event the reporting procedures below should be followed. Any questions concerning adverse event reporting should be directed to the Chief Investigator in the first instance.

8.2.1. Non serious AEs

All such events, whether expected or not, should be recorded- it should be specified if only some non-serious AEs will be recorded, any reporting should be consistent with the purpose of the trial end points.

8.2.2. Serious AEs

An SAE form should be completed and emailed to the Chief Investigator within 24 hours. All SAEs should be reported to the <name of REC> where in the opinion of the Chief Investigator, the event was:

- **'related'**, i.e., resulted from the administration of any of the research procedures; and
- **'unexpected'**, i.e., an event that is not listed in the protocol as an expected occurrence

Reports of related and unexpected SAEs should be submitted within 15 days of the Chief Investigator becoming aware of the event, using the NRES SAE form for non-

IMP studies. The Chief Investigator must also notify the Sponsor of all related and unexpected SAEs. Local investigators should report any SAEs as required by their Local Research Ethics Committee, Sponsor and/or Research & Development Office.

CONTACT DETAILS FOR REPORTING SAEs

[contact]

CI email (and contact details below)

[contact], attention [name]

Please send SAE forms to: [name]

[contact] (Mon to Fri 09:00 – 17:00)

CI: [contact]

[contact]

8.3. THE TYPE AND DURATION OF THE FOLLOW-UP OF SUBJECTS AFTER AE_s

No related SAEs are anticipated as a result of this study. Unexpected SAEs will be managed according to clinical need. Child participants will continue routine clinical care throughout and after the study; routine follow up appointments may be expedited if required due to clinical need as a result of SAEs.

8.4. PREGNANCY

N/A as study involves preschool children

8.5. ANNUAL PROGRESS REPORTS (APR_s)

The Chief Investigator (CI) will prepare the APRs for the study. It will be reviewed by the study site Research Office and sent to the REC by the CI within 30 days of the anniversary date on which the favourable opinion was given by the REC, and annually until the study is declared ended.

8.6. REPORTING URGENT SAFETY MEASURES

The Sponsor and/or the Investigator may take appropriate urgent safety measures in order to protect the subjects of a clinical study against any immediate hazard to their health or safety. If safety measures are taken, REC approval is not required before the measure is taken. The Investigator will immediately and in any event no later than 3 days from the date the measures are taken, give written notice to the REC and the study Sponsor of the measures taken and the circumstances giving rise to those measures. In order to prevent any delays in the reporting timelines the Sponsor has delegated this responsibility to the CI. Therefore, the CI must report any urgent safety measures to the REC directly, and in parallel to the Sponsor. The REC coordinator will acknowledge receipt of urgent safety measures within 30 days.

8.7. MANAGEMENT OF POTENTIAL STUDY RISKS

Child participants routine clinical management is not changed in this observational study. Clinicians have no access to study data. Risks relate to study procedures. All procedures [blood sampling through finger prick test, skin prick tests on either the child's back, leg or arm and FeNO collection (offline method)] will be performed by trained research personnel. Skin prick tests are safe and used clinically for many years, but adrenaline and antihistamines will be available while the study procedures are being performed, in the highly unlikely event of an allergic reaction. All research staff will be trained in management of acute reactions / anaphylaxis. The finger prick test is the same as used by diabetic patients to monitor blood glucose. Collecting breath into a bag is devoid of risk.

9. ASSESSMENT AND FOLLOW-UP

We will arrange for a short monthly electronic questionnaire to be sent by email to the parents/carers, in order to record on a monthly basis, the days their child was out of childcare, days the carer missed from work, unscheduled health care visits and use of rescue therapy or oral corticosteroids (including dosage) (Appendix 4: Monthly Questionnaire). In addition, we will record the children's TRACK™ score (Test for Respiratory and Asthma Control in Kids) (Appendix 3: TRACK™ score questionnaire) every 3 months, to assess wheeze control. There will be review visits every 3 months, to evaluate their progression in person, but if not feasible, video calls will be arranged through Microsoft Teams. In the case of any incidental findings, there will be thorough evaluation of potential benefits or harms before disclosing the information to the child's parent. As this is an observational study, no interventions can be done in the case of incidental findings and parents will be advised to discuss this with their child's GP or paediatrician.

10. END OF STUDY

The end of the study will be when the last of the 100 participants completes his follow-up period of 12 months with his/her last study visit. The anticipated finishing date is December 2023.

11. STATISTICS AND DATA ANALYSIS

The statistical analysis of the project will be done by [name] in collaboration with [name] (University of Edinburgh) and the Asthma UK Centre for Applied Research (AUKCAR), the funder of the study. Statistical analyses will use the GraphPad PRISM software package. A normality test will be performed to assess normal (Gaussian) distribution (e.g., the Shapiro-Wilk test. If there is normal distribution, then parametric tests will be used, otherwise non-parametric tests. Level of significance is set as a p value <0.05. The tests that are currently planned to be used are:

- **Chi-Squared test (x²-test)**

This test allows assessing if a variable is similar between two or more groups or to test if two or more variables are related/dependent

- **Fisher's Exact test**

This test is used when chi-squared values are <5, usually with a small sample size.

- **Student t-test or Mann-Whitney test**

These tests are used for comparison between two study groups. The first is for normally distributed quantitative variables and the second for non-normally distributed quantitative variables.

Data and all appropriate documentation will be stored for a minimum of 10 years after the completion of the study, including the follow-up period.

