The Lancet Asthma Commission has highlighted that 'asthma' is an umbrella term for a clinical syndrome comprising wheeze, chest tightness, breathlessness and sometimes increased cough (2). The focus has moved to defining so-called 'treatable traits', such as whether there is eosinophil airway inflammation, usually driven by the signature Type 2 cytokines Interleukin (IL) -4, -5, and -13, which are responsive to inhaled corticosteroids (ICS) (6,7). Nowhere is this concept of treatable traits more important than in preschool wheeze, wherein only a few children who wheeze have any evidence of allergic sensitisation or Type 2 inflammation. At age one year, even children with such severe symptoms as to merit bronchoscopy in a tertiary referral children's hospital had no evidence of any inflammation or airway remodelling (8). By 30 months of age, in another cross-sectional study, some but by no means all had evidence of eosinophil airway inflammation, reticular basement membrane thickening and airway smooth muscle hypertrophy and hyperplasia (9). Clinical experience reflects this diversity, and although atopic preschool wheezers are more likely to respond to ICS, as we have shown, many atopic wheezers do not have an eosinophil airway phenotype (10), and are thus unlikely to be ICS responsive. We have recently confirmed that there is a good correlation between bronchoalveolar lavage and peripheral blood eosinophil concentrations (11).

Another biomarker for eosinophil airway inflammation is exhaled nitric oxide (FeNO). In older children and adults, titrating ICS dose using FeNO has been shown to reduce asthma attacks and improve outcomes (12). The use of FeNO to guide management not been studied in pre-school children. Young children usually cannot perform the standard slow exhalation, but we have experience in measuring FeNO off-line by collecting tidally exhaled air, which is the technique we propose to use.

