5. STUDY'S AIM AND OBJECTIVES

AIM: To obtain pilot data to test the hypothesis that aeroallergen sensitisation (confirmed by a wheal formation with a diameter ≥ 3 mm after a skin prick test is performed), FeNO (offline method) ≥ 10 ppb and a peripheral blood eosinophil count $\geq 300/\mu\text{l}$, alone or in combination, can predict future wheezing exacerbations in preschool children as well as response to treatment with inhaled corticosteroids, as a preliminary to a large, randomised controlled trial. Also, that these tests are acceptable to families.

OBJECTIVES:

- To recruit 100 preschool children with a history of wheeze, aged one to five years old, and determine atopic status, peripheral blood eosinophil count (point of care test) and FeNO (offline method).
- To evaluate the feasibility and acceptability of these tests
- To categorize the children according to the biomarkers tested and assess whether any or all, alone or in combination, predict future wheezing exacerbations as well as determine the clinical outcome over one year
- To obtain parents' and doctors' insights into whether the biomarkers mentioned above could be used in a future intervention study.

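### Section 11 lets a normality test choose between Student's equal-variance t-test and Mann-Whitney and names no unequal-variance test, so the 0.05 level for the TRACK score is not held if the marker groups differ in both size and spread

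*Combined protocol and SAP*

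**What the plan says.** Section 11 is the whole statistical plan. It opens with a check on the data, "A normality test will be performed to assess normal (Gaussian) distribution (e.g., the Shapiro-Wilk test", and then states the rule: "If there is normal distribution, then parametric tests will be used, otherwise non-parametric tests". For two groups it offers Student's t-test or Mann-Whitney and explains the pair thus: "The first is for normally distributed quantitative variables and the second for non-normally distributed quantitative variables". The level is fixed in one line: "Level of significance is set as a p value <0.05".

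Four things are not stated:
- the significance level of the normality test;
- whether normality is tested on all children together or within each marker group;
- which test belongs to which outcome;
- what happens when the groups have unequal variances.

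The comparisons follow from section 5. The sample size is set by "To recruit 100 preschool children with a history of wheeze, aged one to five years old", and the relevant objective is "To categorize the children according to the biomarkers tested and assess whether any or all, alone or in combination, predict future wheezing exacerbations". Section 4.1 suggests that marker-positive children will be a minority: "wherein only a few children who wheeze have any evidence of allergic sensitisation or Type 2 inflammation".

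**The concern.** Student's test assumes equal variances. A normality test says nothing about that assumption, so data can pass the check and still go to a test whose level is wrong. With equal group sizes this does little harm. With a small marker-positive group against a large negative one, Student's test is too liberal if the small group varies more and too strict if the large group does. In the first case a marker may look predictive by chance more often than the plan states. In the second a real difference is more easily missed. Either would mislead a study meant to supply pilot data for a larger trial.

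There is also a question of consistency. The aim is to see which of three markers, alone or combined, carries information. If normality is checked afresh within each marker split, the same outcome can be compared by means for one marker and by ranks for another, and the results no longer lie on one scale.

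**Working it through.** **Nothing to reproduce.** The documents derive no sample size, power or SD. The only figure is the chosen level of 0.05 (taken as two-sided). The check is whether the planned rule keeps it.

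**Inputs.** From the documents: 100 children, and TRACK as five items of 0 to 20 in steps of 5, so 0 to 100 (Appendix 3). Assumed: marker-positive share 20% or 30%; SDs of 22 and 15 (ratio 22/15 = 1.47); common mean 70; normality tested by Shapiro-Wilk at 0.05.

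**Student's test alone, closed form.** With equal means,

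false-positive rate ≈ 2 × [1 − Φ(1.96 × √(V_pooled / V_true))],

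where V_true = s₁²/n₁ + s₂²/n₂ and V_pooled = s_p² × (1/n₁ + 1/n₂).

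20 v 80, SD 22 v 15:
- V_true = 484/20 + 225/80 = 24.20 + 2.81 = 27.01
- s_p² = (19 × 484 + 79 × 225)/98 = 275.2, so V_pooled = 275.2 × 0.0625 = 17.20
- √(17.20/27.01) = 0.798; 1.96 × 0.798 = 1.564; rate = **11.8%**

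20 v 80, SD 15 v 22:
- V_true = 11.25 + 6.05 = 17.30; s_p² = 433.8; V_pooled = 27.11
- √(27.11/17.30) = 1.252; 1.96 × 1.252 = 2.454; rate = **1.4%**

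The same steps for 30 v 70 give 9.1% and 2.3%. With equal SDs, V_pooled = V_true and the rate is 5.0% at any split.

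**The planned rule, simulated.** 4,000 studies per setting, equal means, normal scores rounded to 5. Student's t is used if normality is not rejected, otherwise Mann-Whitney.

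| Sizes | SDs | Student alone | Rule, normality on all children | Rule, normality within groups | Welch |
|---|---|---|---|---|---|
| 20 v 80 | 22 v 15 | 10.8% | 9.0% | 9.6% | 4.5% |
| 30 v 70 | 22 v 15 | 9.0% | 8.2% | 9.0% | 5.2% |
| 20 v 80 | 15 v 22 | 1.3% | 1.4% | 1.6% | 5.1% |
| 30 v 70 | 15 v 22 | 2.5% | 2.6% | 3.0% | 5.1% |
| 20 v 80 | 15 v 15 | 5.0% | 5.0% | 5.1% | 5.4% |
| 30 v 70 | 15 v 15 | 4.8% | 4.6% | 4.8% | 4.9% |

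Other runs with 20 v 80 and SD 22 v 15 fell between 9.5% and 11.4% for the rule, hence about 9% to 11%. Capping the scores at 100 gave 8.6% (all children) and 10.1% (within groups) at 20 v 80. The cap makes the two means differ slightly, so those two figures are approximate.

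**How far assumptions move the result.** For normal outcomes with 15 to 50 children in the smaller group and SD ratios from 0.5 to 2, the rule ranged from about 0.2% to 21%, and Welch from 4.2% to 5.6%. For a capped TRACK-like score with SD 18 v 15, estimates at 20 v 80 were 6.4% to 6.6% with normality tested on all children, and about 7% to 8% when tested within groups.

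**Which outcomes reach Student's test.** For simulated attack counts (negative binomial with mean 1.5 or 3, Poisson with mean 2), Shapiro-Wilk rejected in essentially every study, so Mann-Whitney was always used. Skewed day counts should behave likewise. TRACK as a score is the outcome left.

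**Different tests for one outcome.** This was simulated with normality tested within each marker split. With 25%, 30% and 40% positive, the three markers did not all get the same test in 44% of studies for a TRACK-like score, 20% for a normal outcome and 0% for a skewed count. With 20%, 30% and 40% positive, a TRACK-like score with mean 65 to 75 gave 24% to 45%, and with mean 80 about 1%. If normality is tested once on all children, every marker gets the same test, missing marker data aside.

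**The case against.** A reader might infer that unequal marker groups are enough to push the error to 11%. They are not: with equal spread the rule stays near 5% at every split tried. The rise needs a smaller group that is also more variable, and no section gives an SD. Section 4.1 does say that "many atopic wheezers do not have an eosinophil airway phenotype", but that concerns airway inflammation. It gives neither the size nor the direction of any difference in the spread of TRACK. It makes unequal spread plausible and no more.

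A reader might also blame the normality test for the inflation. The table does not support this: Student's test alone is at or slightly above the two-stage rule when the smaller group varies more. Deleting the normality test while keeping Student's would leave the problem in place.

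Third, section 11 attaches normality to variables, which reads naturally as one check per outcome on all children. On that reading the point about different tests across markers falls away. It remains possible only because the text does not exclude the other reading.

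Fourth, the reach is narrow. Section 6.1 describes TRACK as an assessment of whether the condition is under control, and Appendix 3 cuts it at 80. It may therefore be analysed as a proportion, and no t-test would arise. The primary outcome is hardly touched by this mechanism.

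All four objections stand as limits. They do not remove the gap: section 11 names no unequal-variance test, and the distortion under unequal spread appears whichever way normality is tested.

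**Conclusion.** The point holds as a conditional one. Section 11 leaves the choice of test to the data, and its parametric option keeps the 0.05 level only if the marker groups have equal spread or equal size. Under the assumed 20 v 80 split with SD 22 v 15, the false-positive rate is about 9% to 11%. With the larger spread in the larger group it is about 2% to 3%, and nearer 1.5% in the uncapped 20 v 80 runs. Neither figure is a prediction or a bound. The cause is the pooled variance, and Welch's test stays close to 5% in the same settings. Mixed tests for one outcome are a further possibility, only under the within-split reading.

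Severity is minor to moderate: it concerns one secondary outcome of a feasibility study, and it is easily corrected before analysis.

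**What to change.** In section 11:

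1. Drop the normality test as the selector. Name one test for each quantitative outcome before data are seen, and use it for all three markers and their combinations.
2. Replace Student's t-test by Welch's t-test, reporting the mean difference and 95% CI for the TRACK score. Keep Mann-Whitney for the skewed day counts, reported as a comparison of distributions and not of means. That caveat matters: for counts with equal means but different dispersion, Mann-Whitney rejected in 20% to 41% of simulated studies.

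The cost is two sentences and a small loss of power when variances are in fact equal. At 20 v 80, Welch's degrees of freedom are 0.0625² / (0.05²/19 + 0.0125²/79) ≈ 29 against 98, so the critical value rises from 1.98 to about 2.04. A comparison with 80% power under Student's test then has about 78%. At 30 v 70 the loss is under one percentage point.

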4.3. PRE-CLINICAL/CLINICAL DATA

This highly variable pathophysiology of pre-school wheeze is reflected in the response to treatment, making the determination of phenotype much more than a matter of academic importance. In the first serious attempt to apply personalised medicine to this group of patients, the INFANT study investigators used a three way crossover design to compare the differential response to therapy with intermittent ICS, regular ICS and montelukast in 300 children (15). Sixty improved spontaneously over the duration of the study. Atopic sensitisation predicted a good response to ICS, shown by reduced numbers of attacks of wheeze and better control of chronic symptoms. In a retrospective analysis, an elevated blood eosinophil count and even better, a combination of positive SPTs and peripheral blood eosinophils $>300/\mu\text{l}$ were the best predictors of a good response to regular ICS. Leukotriene receptor antagonists were not beneficial in any group. Those with no positive SPTs or elevated eosinophil count rarely had acute attacks of wheeze. These findings, especially the predictive power of blood eosinophil count, need to be tested prospectively in primary care, the setting in which most of these children are treated, in a large prospective randomised controlled trial. Prior to this, pilot data to inform power calculations, and the feasibility and

acceptability of this approach needs to be determined. Additionally, although FeNO in preschool children is not well standardized there is one study which proposed FeNO values ≥ 10 ppb to be predictive of eosinophil inflammation in preschool children (16).

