6.1. STUDY OUTCOME MEASURES

Primary outcome:

Acute attacks of wheeze defined as requiring an unscheduled health care visit

Secondary outcomes:

- Carer days off work
- Days the child unable to attend childcare facility
- Use of oral corticosteroids
- Use of inhaled β -2 agonist (rescue therapy)
- Assessment if children's respiratory or wheezing condition is under control by using the TRACK™ score questionnaire (Test for Respiratory and Asthma Control in Kids) (Appendix 3).

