 20	 15	 10	 5	 0	

2. During the past 4 weeks, how often did your child's breathing problems (wheezing, coughing, shortness of breath) wake him or her up at night?
					
Not at all	Once or twice	Once every week	2 or 3 times a week	4 or more times a week	
 20	 15	 10	 5	 0	

3. During the past 4 weeks, to what extend did your child's breathing problems, such as wheezing, coughing or shortness of breath, interfere with his or her ability to play, go to school or engage in usual activities that a child should be doing at his or her age?
					
Not at all	Slightly	Moderately	Quite a lot	Extremely	
 20	 15	 10	 5	 0	

4. During the past 3 months, how often did your need to treat your child's breathing problems (wheezing, coughing or shortness of breath) with quick relief medications (e.g., albuterol, Ventolin®)
					
Not at all	Once or twice	Once every week	2 or 3 times a week	4 or more times a week	
 20	 15	 10	 5	 0	

5. During the past 12 months, how often did you child need to take oral corticosteroids (e.g., prednisone, prednisolone, Decadron®)
					
Not at all	Slightly	Moderately	Quite a lot	Extremely	
 20	 15	 10	 5	 0	

Total Score

Figure 1. The TRACK™ Score Questionnaire. TRACK (Test for Respiratory and Asthma Control in Kids) is a trademark of AstraZeneca group of companies © 2009. TRACK score less than 80 means that the child's breathing problems are out of control. TRACK score above 80 means that the child's breathing problems seem to be in control.

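### As written, Section 11 lets the size of the chi-squared statistic, not the expected cell counts, decide when Fisher's exact test is used, which can change the verdict of individual categorical comparisons

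*Combined protocol and SAP*

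**What the plan says.** Section 11 is the only place where the plan names statistical tests. It gives chi-squared as the general test for categorical data ("This test allows assessing if a variable is similar between two or more groups") and then says of Fisher's exact test: "This test is used when chi-squared values are <5, usually with a small sample size". The threshold is fixed in the same section: "Level of significance is set as a p value <0.05". Sidedness and continuity correction are not stated. Expected cell counts are not mentioned there or anywhere else.

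The objective in Section 5 is to classify children by biomarker and "assess whether any or all, alone or in combination, predict future wheezing exacerbations". Section 6.1 gives the primary outcome as "Acute attacks of wheeze defined as requiring an unscheduled health care visit", without saying whether it is analysed as a count, a yes/no variable or a category. Appendix 4 records emergency appointments in five frequency categories. Appendix 3 gives TRACK a cut-off ("TRACK score less than 80 means that" control is lacking).

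**The concern.** Fisher's test replaces chi-squared when the large-sample approximation is doubtful, that is, when expected counts are small. Expected counts depend only on the table margins. The chi-squared statistic measures how far the data depart from no association, so a rule based on it chooses the test from the result.

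In a 2x2 table the 5% critical value is 3.84, and a statistic of 5 corresponds to p=0.025. Without a correction, the literal rule therefore sends every chi-squared p-value between 0.025 and 0.05 to Fisher, however full the table. It also keeps the approximation in sparse tables whenever the statistic is 5 or more, where it is least reliable.

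Sparse or uneven tables are plausible here. Section 4.1 says that "only a few children who wheeze have any evidence of allergic sensitisation or Type 2 inflammation", and Section 4.3 says of an earlier study: "Those with no positive SPTs or elevated eosinophil count rarely had acute attacks of wheeze". At stake are individual p-values near 0.05, or from very sparse tables, in a study meant to inform a larger trial.

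**Working it through.** **Inputs.** From the documents: N=100 (Section 5), threshold 0.05 and the switching rule (Section 11). Assumed, because the documents give neither biomarker prevalence nor event rate: group splits from 5/95 to 50/50, event rates from 1% to 50%, and two-sided Fisher p-values. The plan has no figure of its own to reproduce.

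**Formulas.** For a 2x2 table with cells a, b (group 1) and c, d (group 2):
- Uncorrected: X² = N(ad − bc)² / (product of the four margins).
- Yates: replace |ad − bc| by |ad − bc| − N/2.
- Smallest expected count = smaller row total × smaller column total / N.

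**Worked examples, 2x2**

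1. *Significance lost, no correction.* 15/30 vs 20/70: ad − bc = 15×50 − 15×20 = 450. X² = 100×450² / (30×70×35×65) = 20,250,000/4,777,500 = 4.24, p=0.040. Smallest expected count = 30×35/100 = 10.5, so chi-squared is adequate. Because 4.24 < 5, the written rule uses Fisher: p=0.066.
2. *Significance gained, no correction.* 2/10 vs 3/90: ad − bc = 2×87 − 8×3 = 150. X² = 100×150² / (10×90×5×95) = 2,250,000/427,500 = 5.26, p=0.022. Smallest expected count = 10×5/100 = 0.5. Because 5.26 ≥ 5, chi-squared is kept; Fisher gives 0.077.
3. *Significance gained, Yates.* 6/30 vs 29/70: |ad − bc| = |6×41 − 24×29| = 450. Corrected X² = 100×(450 − 50)² / 4,777,500 = 3.35, p=0.067, smallest expected count 10.5. Because 3.35 < 5, the written rule uses Fisher: p=0.043.

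**Larger tables.** The 5% critical value is 5.99 on 2 degrees of freedom, 7.81 on 3 and 9.49 on 4 (two groups by five categories). All exceed 5, so a significant chi-squared result is never sent to an exact test. Example with assumed groups of 50, 30, 15 and 5 and with 6, 4, 2 and 3 events: X² = 8.39 on 3 degrees of freedom, p=0.039 kept; exact p=0.075; smallest expected count 5×15/100 = 0.75.

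**Enumeration.** All 2x2 tables for N=100 were enumerated at ten splits. The written rule was compared with the expected-count rule (Fisher if the smallest expected count is below 5). Error rates and power are exact binomial sums. Power without correction, with 50% events in the smaller group and 25% in the larger:

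| Split | Written rule | Expected-count rule | Difference (points) |
|---|---|---|---|
| 5/95 | 20.2% | 19.4% | +0.8 |
| 10/90 | 33.6% | 33.6% | 0.0 |
| 15/85 | 43.6% | 44.0% | −0.4 |
| 20/80 | 51.2% | 58.0% | −6.8 |
| 25/75 | 58.7% | 64.8% | −6.1 |
| 30/70 | 63.8% | 67.8% | −4.0 |
| 35/65 | 67.0% | 72.2% | −5.2 |
| 40/60 | 67.9% | 73.2% | −5.3 |
| 45/55 | 69.9% | 76.0% | −6.1 |
| 50/50 | 67.5% | 74.5% | −7.0 |

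- *Disagreement under the null, no correction:* 0-2.7% of tables at event rates of 10-50%.
- *Where gains arise, no correction:* only with 5 or fewer (or 95 or more) events in 100, except at 5/95.
- *Type I error, no correction, 20/80 to 50/50:* at most 4.4% under the written rule, up to 5.7% under the expected-count rule.
- *Written rule above 5%:* only at 5/95 (6.9% at 2% events, 5.02% at 5%) and 15/85 (6.3% and 5.9% at 1% and 2% events).
- *Yates:* no table loses significance at any split. Gains occur at 15/85 to 45/55 and not at 5/95, 10/90 or 50/50. Type I error stays below 5%.

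**The case against.** The strongest reply is that everyone knows what was meant. The mention of small samples in the same sentence points to sparse data, Section 11 calls these tests only currently planned, and Section 13.3 provides support from a study statistician. The harm arises only if nobody notices the slip. That is fair, and it makes this a wording correction. It does not remove the point, because the text names no other trigger. With the continuity correction also open, more than one p-value could be defended after the data are seen.

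A second reply is that the expected-count rule is not clearly better on error control: it reaches 5.7% where the written rule stays at or below 4.4%. This stands. Part of the lost power is the price of Fisher's conservatism, and Fisher for every 2x2 table would also be a valid rule.

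Four stronger readings are tempting, and the documents or the calculations do not support them:

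- *The rule inflates false positives in general.* The written rule exceeds 5% only in a few very sparse settings with event rates of 5% or less.
- *The primary result is affected.* No section commits wheeze attacks to a categorical test. A count would go to the t-test or Mann-Whitney test, which this rule does not touch.
- *P-values can cross 0.05 both ways whatever the correction.* Losses need an uncorrected chi-squared.
- *Uneven groups are largely spared.* That holds at 15/85 and beyond, but not at 20/80 or 25/75. The remark in Section 4.3 about rare attacks concerns one subgroup of another study and does not show that this cohort will have few events.

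**Conclusion.** The point holds as a defect in a stated analysis rule. As written, the observed statistic selects the test, and no other text corrects it. The effect is confined to individual categorical comparisons that are borderline or very sparse, and its direction depends on a continuity correction that the plan leaves open. All sizes above rest on assumed splits and event rates at N=100. The documents do not show which effect would dominate in this cohort. Confidence is high that the sentence is wrong as it stands. How far it would alter results is much less certain, since the intended rule is probably the conventional one.

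**What to change.** Replace the sentence in Section 11 with: *Fisher's exact test is used when any expected cell count is below 5; otherwise the chi-squared test is used.* Add that the choice is made from the table margins, and state whether a continuity correction applies. Optionally, specify an exact test for sparse tables with more than two groups, if the software supports it.

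The cost is one or two sentences, with no change to data collection or sample size. The price is the slight excess over 5% noted above if no correction is used.
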